2.3 Benefit Risk Assessment

Retinitis Pigmentosa is a group of inherited eye disorders causing slow photoreceptor degeneration, leading to progressive vision loss. Affected patients first experience defective dark adaption, peripheral visual field loss when photoreceptor degeneration progresses, and eventually have only a residual central island of vision, which ultimately progresses to complete blindness. There are currently no approved therapies for the treatment of RP patients with mutations in exon 13 of the *USH2A* gene and disease management is supportive. They may receive adaptive support, when necessary. In addition, patients usually receive genetic counselling on the risks of passing the condition on to their children and regular medical follow up. A significant unmet medical need exists in this sight-threatening condition.

The design of this study has been selected to provide a sufficient benefit-risk ratio to justify the participation of subjects. Planned doses are expected to result in retinal concentrations in the efficacious range. In addition, multiple measures are incorporated to ensure the safety of participating subjects.

To address the potential risks defined in the toxicology studies, the reported risks from oligonucleotides administered by IVT injection, and the risks associated with the IVT injection procedure, extensive monitoring to protect subject safety is incorporated in this study. This will include assessments of subjects' ophthalmic function and anatomy, in particular, monitoring of anterior, intermediate and posterior segment inflammation by slit-lamp biomicroscopy, clinical lens grading using the Age-Related Eye Diseases Study (AREDS) Clinical Lens Grading System, and monitoring for retinal changes by OCT and dilated fundus examinations. This extensive clinical monitoring provides a means to allow early detection of potential AEs, such as macular edema, changes in BCVA and IOP, detection of intraocular inflammation, lens opacities, and retinal structural modifications. In addition, the visit schedule is designed to monitor subjects one day following IVT injection and a second time within 1 week of IVT injection to monitor for signs of endophthalmitis and intraocular inflammation, consistent with guidelines for IVT injections ([Avery 2014](#)).

While the number of subjects is small, these results, and the positive benefit-risk assessment support continued clinical testing of ultevursen.

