8.2.3 Ophthalmic Examinations

Ophthalmic examinations include slit lamp biomicroscopy, intraocular pressure, and dilated fundus examination and will be performed as indicated per the SOE

Further details on the procedures for ophthalmic examinations are in the Study Reference Manual.

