10.9.2 Other Safety Assessments

Other safety assessments, such as ophthalmic examinations and SD-OCT will be summarized and listed as specified in the SAP.

10.10 18-Month Primary Analysis and 24-Month/EOS Analysis

18-Month Primary Analysis

After all randomized subjects have completed their Month 18 visit or discontinued the study prior to this visit, the primary analysis will be conducted, i.e., analysis of the primary and secondary efficacy endpoints at Month 18. Follow-up data beyond 18 months, and available data from other endpoints will be analyzed as well.

24-Month /EOS Analysis

Follow-up data collected post the 18-month treatment period will be presented based on an analysis to be performed after the database is locked once all subjects have reached Month 24.

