### **2.2. Study Termination**

In this context, the Analysis Description (AD) is abbreviated and describes the populations for analysis, data handling rules, statistical methods, and formats for data presentation that will be required for the close out of the study, after all randomized subjects have completed the end of study visit and the database is locked.

The summary tabulations and listings that will be produced for the close out of the study, will provide the basis for the appropriate sections of the abbreviated clinical study report (CSR) or equivalent document.

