## 5.7. Other Data Listings to be Generated

The following by-subject data listings for the Safety Population will be provided:

- Subject Disposition
- Screen Failures (All Screened Subjects)
- Demographic and Baseline Characteristics (Safety Population)
- Non-Ocular Medical History (Safety Population)
- Ocular Medical History (Safety Population)
- Study Drug Administration of the TE (Safety Population)
- Study Drug Administration of the CE (Safety Population)
- BCVA Based on ETDRS (Safety Population)
- Low Luminance Visual Acuity (LLVA) (Safety Population)
- Spectral Domain Optical Coherence Tomography (SD-OCT) (Safety Population)
- Static Perimetry (Safety Population)
- Microperimetry (Safety Population)
- Full Field Stimulus Threshold (FST; Safety Population)
- Patient Global Impressions of Severity (PGI-S) and Patient Global Impressions of Change (PGI-C) (Safety Population)

- Veterans Affairs Low-Vision Visual Functioning Questionnaire – 20 (Safety Population)
- Ophthalmic exam (Safety Population)
- Non-Ocular Adverse Events (Safety Population)
- Ocular Adverse Events (Safety Population)
- Prior and/or Concomitant Medications (Safety Population)
- Laboratory results: Hematology, Coagulation, and Chemistry (Safety Population)

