## **6. CHANGES TO PLANNED ANALYSES**

As the study is prematurely stopped by Sponsor's decision, no formal statistical analysis will be produced. Only disposition, demographic and baseline characteristics, and overview of AEs will be summarized in tables. By-subjects data listings will be produced based on raw data.

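### The close-out SAP lists ophthalmic examinations and SD-OCT without summarizing them by arm, and its table column order leaves out sham

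*SAP*

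**What the plan says.** Protocol 2.3 sets out the monitoring meant to give early detection of "potential AEs, such as macular edema, changes in BCVA and IOP, detection of intraocular inflammation, lens opacities, and retinal structural modifications". The tools it names are slit lamp, AREDS lens grading, OCT and dilated fundus examination. Protocol 8.2.3 adds: "Ophthalmic examinations include slit lamp biomicroscopy, intraocular pressure, and dilated fundus examination and will be performed as indicated per the SOE". Protocol 4.2 applies the same safety monitoring to both eyes.

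For the analysis of these data, Protocol 10.9.2 says: "Other safety assessments, such as ophthalmic examinations and SD-OCT will be summarized and listed as specified in the SAP".

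The SAP explains its scope in 2.2: "In this context, the Analysis Description (AD) is abbreviated". Section 6 gives the reason: "As the study is prematurely stopped by Sponsor's decision, no formal statistical analysis will be produced". It then limits the output: "Only disposition, demographic and baseline characteristics, and overview of AEs will be summarized in tables". In 5.7, the ophthalmic examination and SD-OCT appear as by-subject listings for the Safety Population.

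SAP 5.6 plans AE summaries by treatment group. Ocular AEs are counted by eye, with overviews and SOC/PT tables for the treated and the contralateral eye, and SAEs and AESIs are also summarized. SAP 5.4 fixes the column order of summary tables as ultevursen 180/60 µg, ultevursen 60/60 µg, then all subjects.

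**The concern.** The protocol treats these examinations as its means of finding the ocular harms it expects might occur. A by-subject listing shows each value but gives no rate, shift or distribution by arm. A change in lens grade or IOP that was never entered as an AE would be visible only to a reader who works through the listings and tallies them against treatment assignment.

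The sham arm is the trial's concurrent control for what RP itself does to the eye. Protocol 2.4 states the aim of defining safety and quantifying the effect relative to masked, untreated controls. If measured findings are not summarized by arm, and sham has no column of its own, the close-out report makes poor use of that control.

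**Working it through.** No power, alpha or event-count calculation bears on this point. The check is a comparison of texts and a count of planned outputs.

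**Step 1. Commitment against planned output.**

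| Data | Protocol | SAP |
|---|---|---|
| Ophthalmic examinations (slit lamp, IOP, fundus) | Summarized and listed (10.9.2) | Listing only (5.7) |
| SD-OCT | Summarized and listed (10.9.2) | Listing only (5.7) |
| Ocular AEs | Summarized by treatment group (10.9.1) | Tables by treatment group and eye (5.6) |

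For the first two rows the count is 2 listings and 0 tables by treatment group. For ocular AEs, SAP 5.6 names 2 overviews (one per eye) and 2 SOC/PT tables (one per eye), so 2 + 2 = 4, plus SAE and AESI summaries.

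**Step 2. Does the stated reason cover the omission?** SAP 6 rests on the early stop and the absence of formal analysis. Counts, percentages and summary statistics are not formal analysis. The same SAP tabulates demographics (5.5.2) and AEs (5.6) descriptively, and 5.4 already sets conventions for continuous and categorical variables. The reason explains why hypothesis tests were dropped, but not why these summaries were.

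**Step 3. What is left without a by-arm view?** Protocol 9.2.1 defines an AE broadly enough to take in unfavorable signs found by testing, whatever their cause. A finding recorded as an AE therefore reaches the tables in SAP 5.6. What remains is a measured or graded finding that was not recorded as an AE. The public text gives no rule for when a change in IOP, lens grade or SD-OCT becomes an AE, so the size of that remainder is unknown.

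**Step 4. The column order.** SAP 3.1 and 3.2 have three randomized groups and SAP 5.6 tabulates by treatment group, yet 5.4 names columns for only two of them plus all subjects. Taken literally, sham subjects appear only in the pooled column. At the planned sizes in SAP 3.1 the total is 27 + 27 + 27 = 81, and ultevursen subjects make up (27 + 27) / 81 = 54 / 81 = 66.7% of it. Sham counts could be recovered by subtraction (81 − 27 − 27 = 27 for the denominator, and likewise for event counts). Medians and ranges could not.

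**Step 5. Internal fit of SAP 6.** Section 6 allows an AE overview, which is narrower than the SOC/PT tables in 5.6. Section 6 needs a correction on that account as well.

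**The case against.** The strongest case is that this is a declared reduction in scope. Protocol 10.9.2 defers to the SAP, SAP 2.2 says the document is abbreviated, and SAP 6 states the change and its reason under a heading meant for that purpose. How much to tabulate in an abbreviated report is partly a matter of judgment. AE reporting is also the route the protocol intends for these harms: 2.3 calls them potential AEs, and the only clinical-significance filter visible in 9.4.3 concerns laboratory values. With few subjects and truncated follow-up, complete listings may serve almost as well as tables.

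Much of this stands. Three stronger readings that a reader might infer should be set aside:

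- That the SAP quietly contradicts the protocol. It does not; the reduction is disclosed. But the deferral in 10.9.2 reads more naturally as leaving the form of the summary to the SAP than as permission to drop it, and SAP 6 does not mention 10.9.2.
- That IOP, inflammation, lens and retinal findings go uncompared with sham because they are only listed. Protocol 10.9.2 promises a summary, not a sham comparison, and findings reported as AEs are tabulated by group and eye.
- That sham will certainly be missing from the tables. SAP 5.4 and 5.6 conflict, and the output shells that would settle it are in a separate document (SAP 8).

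It also cannot be said which of these findings the AESI summary would cover, because the public text of Protocol 9.2.4 gives no definition.

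**Conclusion.** The point holds in a limited form. The SAP applies a stated listings-only rule to data that the protocol said would also be summarized, and the reason given does not require it. The loss is the by-arm view of measured ocular findings that were not reported as AEs, for risks named in Protocol 2.3. The omission of sham from the column order in SAP 5.4 is a separate inconsistency within the SAP. It matters more broadly, because it touches every summary table, including the AE tables that serve as the fallback.

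The size cannot be put as a number of hidden findings. The 81 subjects are the planned total; neither the number enrolled nor the follow-up at termination is given. The verdict assumes that the separate shells do not already add these tables or a sham column, and that AREDS lens grades are held with the ophthalmic examination data, since SAP 5.7 names no separate lens listing. No primary conclusion is at risk, because no formal analysis is planned. This is a cheap improvement to the close-out report.

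**What to change.** 1. In SAP 5.4, add the sham procedure to the column order, so that tables show all three randomized groups and then all subjects.
2. In SAP 5.6/5.7, add descriptive summaries for the Safety Analysis Set, by the three groups and by eye (treated, contralateral):
   - IOP and its change from baseline;
   - worst post-baseline shift in AREDS lens grade;
   - worst post-baseline slit-lamp inflammation finding, as recorded (no grading scale is visible in the public text, so none should be presumed);
   - number and percentage with new or worsened macular edema on SD-OCT.
3. In SAP 5.2, add one line defining baseline for these measures, since it now covers only BCVA.
4. Amend SAP 6 to match, including the SOC/PT tables already in 5.6.

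If the sponsor prefers to keep listings only, SAP 6 should at least name the departure from Protocol 10.9.2 and say why descriptive tables were dropped.

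The cost is four summaries for each of two eyes (4 × 2 = 8 panels) from data already due to be listed, with no new collection and no testing. The drawback is that some may be sparse.

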## **8. APPENDICES**

The shells of planned outputs are provided in a separate document (PQ-421a-003\_List of Planned Outputs\_Final\_V1.0 (2022-11-03)).
